## Protocol Synopsis of Study TNP-2092-06

**Title of study:** A Phase 1b/2a, single-center, randomized, double-blind, placebo-controlled study to evaluate the safety, tolerability, pharmacokinetic characteristics, and preliminary efficacy of multiple ascending doses of TNP-2092 Capsules in liver cirrhosis patients with hyperammonemia

**Protocol No.:** TNP-2092-06

**Sponsor:** TenNor Therapeutics (Suzhou) Limited.

**Investigator:** [name], The First Hospital of Jilin University

**Study center:** The study was conducted in a single center in China.

**Study Phase:** 1b/2a

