### **Screening Evaluations**

After signing the written Informed Consent Form, subjects received a series of examinations, including: demographic data (including sex, ethnicity, age, fertility status, weight, height, and BMI), clinical assessment of HE grade, asterixis examination, neuropsychological evaluation, medical history, surgical history, smoking history, alcohol/diet, previous medication, physical examination, vital signs (blood pressure, pulse and body temperature), 12-lead ECG, chest X-ray, abdominal B ultrasound (liver, bile, pancreas and spleen), Fibroscan (transient elastography), clinical laboratory tests (blood ammonia, hematology, blood chemistry, urinalysis, stool routine, coagulation), infectious disease tests (hepatitis B serologic test, hepatitis C antibody, hepatitis C core antigen, HIV antigen/antibody, treponema pallidum antibody, additional RPR test should be performed for those tested positive in treponema pallidum antibody), blood pregnancy test (for females only), to confirm the inclusion criteria and exclusion criteria.

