### **Admission (Baseline) Evaluations**

Admission (baseline) will be occurred on D-1.

Baseline evaluations: Medical history, surgical history, clinical laboratory tests, physical examination, vital signs, 12-lead ECG, serum pregnancy test (females only), urine drug screen, alcohol breath test, fasting blood ammonia concentration, asterixis, Neuropsychological evaluation: Number connection test (NCT-A) and Digit symbol test (DST), Quality of life score (quality of life scale for patients with mild hepatic encephalopathy).

Note: Screening results are valid within 7 days for clinical laboratory tests

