### **Diagnosis and main criteria for inclusion**

Each subject was required to meet all of the following criteria to be eligible for study enrollment:

- 1) 18-65 (inclusive) years of age, male or female.
- 2) Clinically diagnosed with liver cirrhosis.
- 3) Fasting venous blood ammonia above upper limit of normal (ULN).
- 4) Organ functions must meet the following criteria:
  - a) Peripheral blood: absolute neutrophil count  $\geq 0.5 \times 10^9/L$ , platelet  $\geq 20 \times 10^9/L$ , hemoglobin  $\geq 8$  g/dL.
  - b) Liver: aspartate aminotransferase (AST) and alanine aminotransferase (ALT)  $\leq 5 \times$  ULN; serum total bilirubin (TBL)  $\leq 5 \times$  ULN.
  - c) Kidney: creatinine clearance  $\geq 60$  mL/min.
  - d) No malabsorption or other gastrointestinal disorders that affect drug absorption.
- 5) Weight  $\geq 45$  kg and body mass index [BMI = weight (kg)/height (m^2) ] between 18 and 34 (inclusive) kg/m^2.
- 6) Subjects (including their partners) will have no pregnancy plan and voluntarily take effective contraceptive measures within 6 months after drug withdrawal. Refer to Appendix 9 for specific contraceptive measures.

- 7) Subjects or their legal representatives sign the Informed Consent Form and fully understand the content, procedures, and potential adverse reactions prior to the initiation of the study.
- 8) Able to complete the study per the requirements in the study protocol.

Subjects meeting any of the following criteria were ineligible for study enrollment:

- 1) Subjects who are allergic to rifamycin or quinolone antibacterial agents or those with an allergic constitution.
- 2) Pregnant or lactating women, or women of childbearing age with a positive pregnancy test from the screening period to initiation of the study treatment.
- 3) Subjects with serious nervous or mental disorders.
- 4) Subjects with Child-Pugh class C liver cirrhosis.
- 5) Subjects with Grade 2 or above hepatic encephalopathy.
- 6) Subjects who have been diagnosed with *Clostridium difficile*-induced pseudomembranous enteritis within 3 months.
- 7) Subjects who have had systemic infection or gastrointestinal bleeding within 7 days prior to screening.
- 8) Subjects with clinically significant abnormal clinical laboratory tests or other clinical findings indicative of clinically significant disorders that, in the opinion of the investigator, make them not eligible for this clinical study.

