For HE grades, Wilcoxon signed rank test will be used to determine whether changes from baseline in each treatment group are different on D7 or D15. Wilcoxon rank sum test will be used to determine whether changes on D7 and D15 are different between treatment groups and between each treatment group and the control group.

If D7 or D15 data are missing, the last observation carried forward (LOCF) approach will be used for imputation.

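### Does the hepatic encephalopathy (HE) grade analysis fail because the D-1 baseline list leaves the grade out?

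*Combined protocol and SAP*

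**What the plan says.** The Efficacy Evaluation section lists the clinical grade of HE as an efficacy measure. The Efficacy analysis section calculates change from baseline for every endpoint except asterixis. For this endpoint it adds: "For HE grades, Wilcoxon signed rank test will be used to determine whether changes from baseline in each treatment group are different on D7"; the same applies to D15. A rank sum test then compares the changes between groups, and missing D7 or D15 values are filled by last observation carried forward.

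The Admission (Baseline) Evaluations section fixes the visit: "Admission (baseline) will be occurred on D-1". Its efficacy items are "fasting blood ammonia concentration, asterixis, Neuropsychological evaluation: Number connection test (NCT-A) and Digit symbol test (DST), Quality of life score"; HE grade is not among them. The Screening Evaluations section does include it: "clinical assessment of HE grade, asterixis examination, neuropsychological evaluation". The only rule on reusing screening results is "Note: Screening results are valid within 7 days for clinical laboratory tests".

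One exclusion criterion is "Subjects with Grade 2 or above hepatic encephalopathy". The text is headed "Protocol Synopsis of Study TNP-2092-06", and it refers to an appendix that is not part of it.

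**The concern.** A change score needs a defined starting value. Here the baseline visit is D-1, the D-1 list has every other visit-based efficacy measure, and HE grade is absent. Screening names HE grade separately from asterixis and neuropsychological evaluation, and the D-1 list spells out the latter as NCT-A and DST. So neither item can be read as covering the grade.

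If the screening grade becomes the baseline by default, the same reading may both admit the patient and start the change score. Only patients reading below Grade 2 at that moment get in. Later readings are not capped, so the average grade tends to rise with no drug effect. The within-arm change would then lean towards worsening and hide part of a true improvement. A D-1 grade that was not taken cannot be recovered later.

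**Working it through.** **1. Is the baseline really undetermined?** There are two possibilities.

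- HE is graded at screening only. There is then one pre-dose grade and nothing to choose between.
- HE is also graded on D-1, and the synopsis list is incomplete. The admission section already equates D-1 with baseline, so the D-1 grade is used.

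In both cases the last grade before dosing is the baseline. The carry-forward rule raises no separate difficulty: if D7 is missing and the pre-dose grade is carried, the change is zero under either reading.

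**2. Does the choice affect the comparison with placebo?** Let S be the baseline grade and Y the D15 grade, with T for drug and P for placebo.

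Mean contrast = (E[Y|T] − E[S|T]) − (E[Y|P] − E[S|P])

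Within a dose group patients are randomised 2:1, and S is measured before dosing, so E[S|T] = E[S|P]. The contrast reduces to E[Y|T] − E[Y|P], which does not contain S. With no drug effect the changes have the same distribution in both arms, so the rank sum test keeps its error rate. If placebo patients are pooled across dose groups, the cohorts must also be comparable, whichever grade is the baseline.

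**3. How large could the within-arm drift be?** The documents give neither the mix of grades at screening nor the correlation between repeated grades. All inputs here are assumptions. The model is a latent normal scale cut into grades 0/1/2/3+, with selection on a screening grade below 2.

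One cell in full, with a mix of 40/35/20/5% and correlation 0.5:

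- mean screening grade of those admitted = 35/(40 + 35) = 0.467
- mean D15 grade with no drug effect = 0.716
- drift = 0.716 − 0.467 = +0.249
- with a true improvement of 0.5 SD, within-arm change = −0.078
- contrast with placebo = −0.078 − 0.249 = −0.327

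The contrast recovers the whole effect. Across the assumed range, correlation 0.5 to 0.95:

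| Grade 2 or above among those screened | Drift, screening baseline | Share of a 0.5 SD improvement masked within arm |
|---|---|---|
| 10-25% (four mixes) | +0.02 to +0.25 | 11-76% |
| 3% | +0.01 to +0.04 | 5-26% |

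The larger figures need a correlation near 0.5. At 0.95, the four mixes give 11-17% masked.

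**4. Would a D-1 grade remove the drift?** Only if correlation between visits does not fall with time and the D-1 grade is not itself used to exclude. If the exclusion is applied again on D-1, 56-82% of the drift remains. If correlation decays with time, 51-62% remains.

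**5. Would any within-arm test decision change?** The exact signed rank test drops zero changes. With k non-zero changes the smallest two-sided p-value is 2 × 0.5^k.

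- k = 4: 0.125
- k = 5: 0.0625
- k = 6: 0.031

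So at least 6 of the 8 treated patients must change grade, all or nearly all in one direction. A single group's 4 placebo patients can never reach 0.05. Simulated rejection rates at n = 8 are 0-1.2% with no effect and 0.1-2.2% at 0.5 SD, over both baselines.

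**The case for a change.** The best argument for acting is that a pre-specified test lacks a stated input, the remedy is one sentence, and a grading not done on D-1 is lost. The omission is also selective: every other visit-based efficacy measure is on the D-1 list, and the 7-day note covers laboratory tests only. Nor does the eligibility wording, "Subjects meeting any of the following criteria were ineligible for study enrollment", say which pre-dose HE grade the criterion refers to.

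These observations are correct, and a sentence naming the baseline grade would be tidier. They do not show that the analysis goes wrong. A synopsis that lists all the companion measures, and then tests change in HE grade, may simply have an incomplete list; the visit schedule that would settle this is not in the text. If D-1 grading does take place, nothing is lost. If it does not, the sole pre-dose value is used, and its bias runs against the drug and appears in the placebo arm too. Parts of the synopsis are in the past tense, so an added assessment may no longer be possible, although the tenses are mixed. The calculations above also show that a D-1 grade might remove less than half of the drift.

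**Conclusion.** No change to the plan follows. This is a missing detail that an analyst fills sensibly by using the last grade before dosing. HE grade is one secondary endpoint in a study whose primary objectives are safety, tolerability and pharmacokinetics.

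The mean comparison with placebo inside a dose group does not depend on the baseline chosen, by randomisation alone. No false signal of efficacy arises, and the within-arm test is too small for the choice to alter its outcome in practice. What remains is a possible lean towards worsening in a descriptive within-arm mean, if the screening grade is used. The documents do not allow that lean to be estimated: +0.01 to +0.25 grade spans the assumed inputs tried and does not bound the truth. Anyone reading the within-arm HE changes should set them beside the placebo arm, where the same drift is expected.

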**PK analysis:**

Plasma drug concentration (c)-time (t) data will be summarized by dose group and time point and c-t curves plotted based on the PK concentration set. PK parameters for the first dose (Day 1) and the last dose (Day 15) will be calculated by a non-compartmental model using Phoenix WinNonLin (version 8.3), including:  $T_{max}$ ,  $C_{max}$ ,  $t_{1/2}$ ,  $AUC_{0-\infty}$ ,  $AUC_{0-last}$ ,  $AUC_{0-tau}$  and  $CL/f$ . In addition, the accumulation index will also be calculated:  $AUC_{0-tau}(D15)/AUC_{0-tau}(D1)$ ;  $C_{max}(D15)/C_{max}(D1)$ . Each parameter will be summarized by dose group based on the PK parameter analysis set. PK concentrations and PK parameters for each subject will be listed.

**Safety analysis:**

Adverse events will be coded using the latest medical dictionary MedDRA. All treatment emergent adverse events, serious adverse events, study drug-related adverse events and adverse events leading to withdrawal will be summarized by treatment group, system organ class and preferred term based on the safety analysis set. The number and percentage of subjects for each category of adverse events and the number of adverse events will be calculated. All adverse events will be listed. Laboratory tests, 12-lead ECG, vital signs and physical examination results will be summarized by treatment group and visit and listed. Where appropriate, cross tabulations will be used to reflect changes from baseline in post-baseline test/examination results.
